## 4 RESEARCH QUESTION AND OBJECTIVES

The primary objective of this study is to estimate the incidence of the select medical events of interest, those being the 8 System Organ Classes (SOCs) and 3 Standardized MedDRA Queries (SMQs) listed below, in pediatric patients after treatment with higher IV LCM doses, compared to pediatric patients treated with recommended initial/maintenance IV LCM dose:

- Cardiac disorders

- 
- Skin and subcutaneous tissue disorders
  - Nervous system disorders
  - Metabolism and nutrition disorders
  - Psychiatric disorders
  - Injury, poisoning and procedural complications
  - General disorders and administration site conditions
  - Investigations of ECG indicating long PR
  - Drug reaction with eosinophilia and systemic symptoms syndrome
  - Severe cutaneous adverse reactions
  - Hypersensitivity

The secondary objectives of this study are:

1. To estimate the incidence of the selected medical events included in the 8 System Organ Classes (SOC) and 3 Standardized MedDRA Queries (SMQs) as indicated below, in pediatric patients after treatment with higher than the recommended IV LCM doses, compared to pediatric patients treated with recommended initial/maintenance IV LCM dose.
- Cardiac disorders
    - Atrioventricular block
    - Atrioventricular block complete
    - Atrioventricular block first degree
    - Atrioventricular block second degree
    - Arrhythmia
    - Bradyarrhythmia
    - Bradycardia
    - Cardiac fibrillation
    - Cardiac flutter
    - Tachyarrhythmia
    - Atrial fibrillation
    - Atrial flutter
    - Cardiac arrest
    - Torsade de pointes
    - Ventricular arrhythmia
    - Ventricular fibrillation
    - Ventricular tachyarrhythmia
    - Palpitations
  - Skin and subcutaneous tissue disorders
    - Stevens-Johnson syndrome
    - Toxic epidermal necrolysis
    - Angioedema
    - Urticaria

- Pruritus
  - Rash
  - Nervous system disorders
    - Dizziness
    - Somnolence
    - Paresthesias
    - Loss of consciousness
    - Syncope
  - Metabolism and nutrition disorders
    - Appetite disorder
    - Decreased appetite
    - Diet refusal
    - Hypophagia
    - Food aversion
  - General disorders and administration site conditions
    - Chest pain
    - Gait disturbances
  - Injury, poisoning and procedural complication
    - Injection site discomfort
    - Injection site erythema
    - Injection site irritation
    - Injection site pain

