## **5.5 Variables**

### **5.5.1 Primary outcome measure**

The following primary variables will be measured to meet the study objectives:

- The incidence rate and incidence rate ratio of cardiac disorders (selected preferred terms (PTs) as described in Section 5.5.5)
- The incidence rate and incidence rate ratio of general disorders and administration site conditions (selected PTs as described in Section 5.5.5)
- The incidence rate and incidence rate ratio of injury, poisoning and procedural complications (selected PTs as described in Section 5.5.5)
- The incidence rate and incidence rate ratio of investigations (i.e. the incidence rate of ECG PR prolongation)
- The incidence rate and incidence rate ratio of skin and subcutaneous tissue disorders (selected PTs as described in Section 5.5.5)
- The incidence rate and incidence rate ratio of drug reactions with eosinophilia and systemic symptoms syndrome (selected PTs as described in Section 5.5.5)
- The incidence rate and incidence rate ratio of severe cutaneous adverse reactions (selected PTs as described in Section 5.5.5)
- The incidence rate and incidence rate ratio of hypersensitivity (selected PTs as described in Section 5.5.5)
- The incidence rate and incidence rate ratio of nervous system disorders (selected PTs as described in Section 5.5.5)
- The incidence rate and incidence rate ratio of metabolism and nutrition disorders (selected PTs as described in Section 5.5.5)

- The incidence rate and incidence rate ratio of psychiatric disorders (i.e. abnormal behavior)

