### **5.5.2 Secondary outcome measure**

The secondary variables that will be evaluated in this study include:

- Incidence rate and incidence rate ratio of atrioventricular block
- incidence rate and incidence rate ratio of atrioventricular block complete
- incidence rate and incidence rate ratio of atrioventricular block first degree
- incidence rate and incidence rate ratio of atrioventricular block second degree
- incidence rate and incidence rate ratio of arrhythmia
- incidence rate and incidence rate ratio of bradyarrhythmia
- incidence rate and incidence rate ratio of bradycardia
- incidence rate and incidence rate ratio of cardiac fibrillation
- incidence rate and incidence rate ratio of cardiac flutter
- incidence rate and incidence rate ratio of tachyarrhythmia
- incidence rate and incidence rate ratio of atrial fibrillation
- incidence rate and incidence rate ratio of atrial flutter
- incidence rate and incidence rate ratio of cardiac arrest
- incidence rate and incidence rate ratio of torsade de pointes
- incidence rate and incidence rate ratio of ventricular arrhythmia
- incidence rate and incidence rate ratio of ventricular fibrillation
- incidence rate and incidence rate ratio of ventricular tachyarrhythmia
- incidence rate and incidence rate ratio of palpitations
- incidence rate and incidence rate ratio of chest pain
- incidence rate and incidence rate ratio of gait disturbances
- incidence rate and incidence rate ratio of injection site discomfort
- incidence rate and incidence rate ratio of injection site erythema
- incidence rate and incidence rate ratio of injection site irritation
- incidence rate and incidence rate ratio of injection site pain
- incidence rate and incidence rate ratio of stevens-johnson syndrome
- incidence rate and incidence rate ratio of toxic epidermal necrolysis
- incidence rate and incidence rate ratio of angioedema
- incidence rate and incidence rate ratio of urticaria

- incidence rate and incidence rate ratio of pruritus
- incidence rate and incidence rate ratio of rash
- incidence rate and incidence rate ratio of dizziness
- incidence rate and incidence rate ratio of somnolence
- incidence rate and incidence rate ratio of paresthesias
- incidence rate and incidence rate ratio of loss of consciousness
- incidence rate and incidence rate ratio of syncope
- incidence rate and incidence rate ratio of appetite disorder
- incidence rate and incidence rate ratio of decreased appetite

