Electrocardiographic ventricular fibrillation (finding)	SCTID: 164896001
Chronic atrial fibrillation (disorder)	SCTID: 426749004
Paroxysmal atrial fibrillation (disorder)	SCTID: 282825002
Persistent atrial fibrillation (disorder)	SCTID: 440059007
Preexcited atrial fibrillation (disorder)	SCTID: 762247006
Atrial fibrillation and flutter (disorder)	SCTID: 195080001
Non-rheumatic atrial fibrillation (disorder)	SCTID: 233911009
Sustained ventricular fibrillation (disorder)	SCTID: 429243003
Lone atrial fibrillation (disorder)	SCTID: 233910005
Ventricular fibrillation and flutter (disorder)	SCTID: 195083004
Permanent atrial fibrillation (disorder)	SCTID: 440028005

Table 3 SNOMED-CT concepts for the study	
Study outcome	SNOMED code
Cardiac flutter	
Fluttering heart (finding) *	SCTID: 161969004
Ventricular fibrillation and flutter (disorder)	SCTID: 195083004
Atrial fibrillation and flutter (disorder)	SCTID: 195080001
Tachyarrhythmia (disorder)	SCTID: 6285003
Atrial fibrillation	SCTID: 49436004
Atrial fibrillation and flutter (disorder)	SCTID: 195080001
Paroxysmal atrial fibrillation (disorder)	SCTID: 282825002
Rapid atrial fibrillation (disorder)	SCTID: 314208002
Electrocardiographic atrial fibrillation (finding)	SCTID: 164889003
Chronic atrial fibrillation (disorder)	SCTID: 426749004
Persistent atrial fibrillation (disorder)	SCTID: 440059007
Preexcited atrial fibrillation (disorder)	SCTID: 762247006
Atrial fibrillation and flutter (disorder)	SCTID: 195080001
Non-rheumatic atrial fibrillation (disorder)	SCTID: 233911009
Lone atrial fibrillation (disorder)	SCTID: 233910005
Ventricular fibrillation and flutter (disorder)	SCTID: 195083004
Permanent atrial fibrillation (disorder)	SCTID: 440028005
Atrial flutter	SCTID: 5370000
Electrocardiographic atrial flutter (finding)	SCTID: 164890007
Typical atrial flutter (disorder)	SCTID: 720448006
Atypical atrial flutter (disorder)	SCTID: 15964901000119107
Cardiac arrest	SCTID: 410429000
Neonatal cardiac arrest (disorder)	SCTID: 180906006
Bradycardic cardiac arrest (disorder)	SCTID: 703162001
Cardiac arrest due to cardiac disorder (disorder)	SCTID: 423191000
Torsade de pointes	SCTID: 31722008
Electrocardiographic torsades de pointes (finding)	SCTID: 426882006
Ventricular arrhythmia	SCTID: 44103008
Electrocardiographic ventricular arrhythmia (finding)	SCTID: 164893009
Ventricular fibrillation	SCTID: 71908006

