Electrocardiographic ventricular fibrillation (finding)	SCTID: 164896001
Sustained ventricular fibrillation (disorder)	SCTID: 429243003
History of ventricular fibrillation (situation)	SCTID: 161513002
Ventricular tachyarrhythmia (disorder)	SCTID: 6624005
Palpitations (finding)	SCTID: 80313002
Palpitations - rapid (finding)	SCTID: 248648003
Bumping heart (finding)	SCTID: 161968007

Table 3 SNOMED-CT concepts for the study	
Study outcome	SNOMED code
Pounding heart (finding)	SCTID: 248657009
Fluttering heart (finding) *	SCTID: 161969004
Palpitations with regular rhythm (finding)	SCTID: 428919002
Intermittent palpitations (finding)	SCTID: 102590007
History of palpitations (situation)	SCTID: 473122004
Skin and subcutaneous tissue disorders	
Stevens-Johnson syndrome (disorder)	SCTID: 73442001
Stevens-Johnson syndrome caused by drug (disorder)	SCTID: 403609001
Stevens-Johnson syndrome, toxic epidermal necrolysis spectrum (disorder)	SCTID: 768946000
Stevens Johnson syndrome AND toxic epidermal necrolysis overlap (disorder)	SCTID: 124911000119100
Stevens-Johnson and toxic epidermal necrolysis overlap syndrome caused by drug (disorder)	SCTID: 724833000
Toxic epidermal necrolysis	
Lyell syndrome (disorder)	SCTID: 768962006
Toxic epidermal necrolysis caused by drug (disorder)	SCTID: 402744003
Stevens-Johnson syndrome, toxic epidermal necrolysis spectrum (disorder)	SCTID: 768946000
Stevens Johnson syndrome AND toxic epidermal necrolysis overlap (disorder)	SCTID: 124911000119100
Stevens-Johnson and toxic epidermal necrolysis overlap syndrome caused by drug (disorder)	SCTID: 724833000
Angioedema	SCTID: 41291007
Giant urticaria (disorder)	SCTID: 400075008
Drug-aggravated angioedema-urticaria (disorder)*	SCTID: 241958006
Angioedema and/or urticaria (disorder)*	SCTID: 404177007
Urticaria	SCTID: 126485001
Acute urticaria (disorder)	SCTID: 402408009
Chronic urticaria (disorder)	SCTID: 51611005
Allergic urticaria (disorder)	SCTID: 40178009
Immunologic urticaria (disorder)	SCTID: 40370006
Contact urticaria (disorder)	SCTID: 19364004
Allergic contact urticaria (disorder)	SCTID: 402304007
Urticaria medicamentosa (disorder)	SCTID: 11012891000119106
Urticaria caused by serum (disorder)	SCTID: 89322006
Drug-aggravated angioedema-urticaria (disorder)*	SCTID: 241958006
Angioedema and/or urticaria (disorder)*	SCTID: 404177007

Table 3 SNOMED-CT concepts for the study	
Study outcome	SNOMED code

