Skin sensation disturbance (finding)	SCTID: 80910005
Complaining of paresthesia (finding)	SCTID: 31048100
Loss of consciousness	
Loss of consciousness (finding)	SCTID: 419045004
Brief loss of consciousness (finding)	SCTID: 32834005
Moderate duration loss of consciousness (finding)	SCTID: 40863000
Prolonged loss of consciousness (finding)	SCTID: 7862002
Syncope	SCTID: 271594007
Syncope and collapse (disorder)	SCTID: 309585006
Metabolism and nutrition disorders	
Appetite disorder	
Non-organic loss of appetite (disorder)	SCTID: 192017004
Appetite problem (finding)	SCTID: 289163007
Appetite symptom (finding)	SCTID: 161824009
Centrally acting appetite suppressant adverse reaction (disorder)	SCTID: 292259006
Altered appetite (finding)	SCTID: 249473004
Eating disorders management (procedure)	SCTID: 386264009
Decrease in appetite (finding)	SCTID: 64379006
Non-organic loss of appetite (disorder)	SCTID: 192017004

Table 3 SNOMED-CT concepts for the study	
Study outcome	SNOMED code
Decreased appetite Decrease in appetite (finding)	SCTID: 64379006
Diet refusal Refusing food (finding) Does not eat (finding) Unable to eat (finding)	SCTID: 105481005 SCTID: 288887001 SCTID: 288885009
Hypophagia Decrease in appetite (finding) Non-organic loss of appetite (disorder)	SCTID: 64379006 SCTID: 192017004
Food aversion Aversion to food or drink (finding) Finding of food aversion and cravings (finding) Sensory aversion to particular foods (finding) Aversion to particular food (finding)	SCTID: 248134002 SCTID: 289143000 SCTID: 16230791000119104 SCTID: 248135001
General disorders and administration site conditions	

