Erythema at injection site (disorder)	SCTID: 213338000
Injection site irritation	
Injection site irritation (disorder)	SCTID: 95379009
Injection site pain	
Injection site pain (disorder)	SCTID: 95388000

Table 3 SNOMED-CT concepts for the study	
Study outcome	SNOMED code
Psychiatric disorders	
Abnormal behavior (finding)	SCTID: 25786006
Mildly abnormal behavior (finding)	SCTID: 165311008
Severely abnormal behavior (finding)	SCTID: 165312001
Drug reaction with eosinophilia and systemic symptoms Syndrome	
Drug reaction with eosinophilia and systemic symptoms Syndrome (disorder)	SCTID: 702809001
Acute generalized exanthematous pustulosis (disorder)	SCTID: 702617007
Severe cutaneous adverse reactions	
Drug reaction with eosinophilia and systemic symptoms Syndrome (disorder)	SCTID: 702809001
Acute generalized exanthematous pustulosis (disorder)	SCTID: 702617007
Lyell syndrome (disorder)	SCTID: 768962006
Toxic epidermal necrolysis caused by drug (disorder)	SCTID: 402744003
Stevens-Johnson syndrome, toxic epidermal necrolysis spectrum (disorder)	SCTID: 768946000
Stevens Johnson syndrome AND toxic epidermal necrolysis overlap (disorder)	SCTID: 124911000119100
Stevens-Johnson and toxic epidermal necrolysis overlap syndrome caused by drug (disorder)	SCTID: 724833000
Stevens-Johnson syndrome (disorder)	SCTID: 73442001
Stevens-Johnson syndrome caused by drug (disorder)	SCTID: 403609001
Cutaneous hypersensitivity (disorder)	SCTID: 21626009
Hypersensitivity	
Non-allergic drug hypersensitivity disorder (disorder)	SCTID: 427640001
Hypersensitivity disease of liver caused by drug (disorder)	SCTID: 735456000
Renal hypersensitivity caused by drug (disorder)	
Allergic reaction, caused by correct medicinal substance properly administered (disorder)	SCTID: 762531008
	SCTID: 57302007
Drug reaction with symptoms ( eosinophilia and systemic disorder)	SCTID: 702809001

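### Used as printed, the Section 5.5.5 outcome lists and Table 3 count a rash code as a severe skin reaction, count a ventricular code as atrial fibrillation, and leave the administration-site outcome without a site event

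*Protocol*

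**What the plan says.** The primary measures in Protocol Section 5.5.1 are rates and rate ratios for eleven broad outcomes, most of them defined by pointing to Section 5.5.5. For the severe skin outcome the text is "The incidence rate and incidence rate ratio of severe cutaneous adverse reactions (selected PTs as described in Section 5.5.5". Section 5.5.2 then names single events as secondary measures, for example "incidence rate and incidence rate ratio of atrial fibrillation", with a separate line for ventricular fibrillation.

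Section 5.5.5 holds the event lists and the code list (Table 3). Three places matter:

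- **Skin.** "Cutaneous hypersensitivity (disorder" (SCTID 21626009) closes the Rash block and also closes the Severe cutaneous adverse reactions block.
- **Rhythm.** "Ventricular fibrillation and flutter (disorder" (SCTID 195083004) stands in the Atrial fibrillation block, between the lone and the permanent atrial forms. It also stands under Cardiac fibrillation and Cardiac flutter.
- **Injection site.** "Injection site discomfort" and the three other injection-site terms are the only events under the Injury, poisoning and procedural outcome. The general disorders and administration-site outcome lists chest pain and gait disturbances only. Section 4, the event list in Section 5.5.5 and Table 3 agree on this placement.

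Section 5.5.5 also says that no validated algorithms exist, that the Table 3 concepts are still to be reviewed and turned into case definitions with clinicians, and that sensitivity analyses will test those definitions.

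**The concern.** This is a safety study whose results are rates per outcome, so a code in the wrong list goes straight into a reported rate. Severe skin reactions are expected to be rare. One non-severe code without a severity condition could supply most of the counted cases, producing apparent severe reactions and diluting a real dose effect. Under Section 5.9.1.2 only the first event counts and person-time stops there, so an early rash code would also pre-empt a later true severe reaction in the same child.

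The ventricular code would put a ventricular event into the atrial rate. For the third item, a reader who looks up the administration-site rate of an intravenous drug would find a figure with no site event in it, and the injection-site events under Injury.

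**Working it through.** The Protocol states no expected rate, power or derived sample size for these outcomes (Section 5.9.3 gives a feasibility count of 875), so there is no planned figure to reproduce. The check compares the Table 3 blocks with one another and with Sections 4, 5.5.1 and 5.5.2.

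**1. Severe cutaneous adverse reactions.** The block has 10 codes. Removing every code that also stands in the Stevens-Johnson, toxic epidermal necrolysis or DRESS blocks leaves exactly one, 21626009. That code is in the Rash block and is not in the Hypersensitivity block. The Protocol therefore classes it as rash in one place and as severe in another, and nothing separates the two uses.

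**2. Atrial and ventricular fibrillation.** The Atrial fibrillation block has 13 rows and 12 distinct codes (195080001 appears twice). Eleven are atrial; the twelfth is 195083004. The Ventricular fibrillation block has four codes: 71908006, 164896001, 429243003 and 161513002 ("History of ventricular fibrillation (situation"). 195083004 is not among them, nor is it under Ventricular arrhythmia. The corresponding combined atrial code, 195080001, is listed under Atrial fibrillation, so by the table's own pattern the combined ventricular code belongs under Ventricular fibrillation. Because 195083004 is a cardiac code in either place, the primary Cardiac rate is the same before and after correction.

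**3. Administration site.**

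| Primary outcome | Events listed in Sections 4 and 5.5.5 |
|---|---|
| General disorders and administration site | chest pain; gait disturbances |
| Injury, poisoning and procedural | injection-site discomfort, erythema, irritation, pain |

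The first outcome holds no site event and the second holds nothing else. Two site codes also appear elsewhere in Table 3 (injection-site paresthesia under Paresthesia, application-site rash under Rash), but none is under the administration-site outcome.

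**4. Illustration of the dilution in item 1.** All risks here are assumptions; none is in the Protocol. Let s be the true severe-reaction risk and r the risk of code 21626009 in the comparator group, with no overlap and equal person-time. Take a true rate ratio of 3 for severe reactions and 1 for the added code.

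True share of counted comparator cases = s/(s + r). Observed ratio = (3s + 1·r)/(s + r).

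| s | r | True share | Observed ratio |
|---|---|---|---|
| 0.05% | 0.2% | 0.0005/0.0025 = 20% | 0.0035/0.0025 = 1.40 |
| 0.05% | 2% | 0.0005/0.0205 = 2.4% | 0.0215/0.0205 = 1.05 |
| 0.1% | 1% | 0.001/0.011 = 9.1% | 0.013/0.011 = 1.18 |
| 0.2% | 0.2% | 0.002/0.004 = 50% | 0.008/0.004 = 2.00 |
| 0.2% | 2% | 0.002/0.022 = 9.1% | 0.026/0.022 = 1.18 |

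Over the grid s = 0.05% to 0.2% and r = 0.2% to 2%, the true share runs from about 2% to 50% and the observed ratio from 1.05 to 2.00. The observed ratio is a weighted average, so it is pulled towards whatever ratio the rash code itself has.

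**The case against.** The strongest reply is that Table 3 is an input, not the final case definition. Section 5.5.5 foresees a review of the concepts, Section 5.1 adds procedure and medication codes where needed, Section 5.4.1 leaves the reporting level to be agreed with safety physicians, and Section 5.9.1.4 plans a sensitivity analysis on outcome definitions. This stands as a limit: a reader might infer that the rates are already wrong, and the Protocol does not show that. It does not remove the point. The review is of the Table 3 concepts, whereas the injection-site placement is also fixed in the objectives. The sensitivity analysis requires an added medication or procedure code and does not re-map codes. Chart review is promised for all eligible patients in Section 5.1 but for about 10% in Section 5.4.1, so it cannot be relied on to correct every case.

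Other stronger readings also fail:

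- **Ventricular events are missed by the study.** They are not. 195083004 still counts under Cardiac fibrillation, Cardiac flutter and the primary Cardiac outcome.
- **Injection-site events are lost.** They are not. Each of the four is a secondary measure and all count in one primary outcome. The lists agree with one another; the conflict is between an outcome's name and its content.
- **"Acute generalized exanthematous pustulosis (disorder" is misplaced under DRESS.** The documents do not settle this. The severe cutaneous list is an umbrella that repeats both DRESS-block codes, so a separate entry there proves nothing.
- **An invalid identifier undermines the paresthesia outcome.** The code 31048100, beside "Complaining of paresthesia (finding", fails the check digit, but a dropped final digit or a PDF artefact would explain it, and the block also holds the general paresthesia code.
- **A number of false severe cases can be stated.** It cannot. That needs the cohort size and the frequency of the code, and Section 5.9.3 offers only 875 before full criteria and several hundred after.

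**Conclusion.** The point holds conditionally: if the Section 5.5.5 lists and Table 3 are used as printed, three mappings are wrong.

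- The primary severe-skin rate takes in a code that the Protocol itself lists as rash. It could be inflated and its rate ratio diluted. The 1.05 to 2.00 range rests wholly on the assumed risks and ratios above; the actual size cannot be computed from the documents.
- The secondary atrial fibrillation rate is overcounted and the ventricular fibrillation rate undercounted, each by the events carrying one code.
- Two primary outcomes, administration site and Injury, are mislabelled, with no event lost.

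The primary Cardiac rate and the overall any-event rate in Section 5.9.1.2 do not change, since every code concerned still counts as an event of interest somewhere. The correction should be made because it touches primary safety outcomes and costs little.

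**What to change.** 1. Remove 21626009 from Severe cutaneous adverse reactions and keep it under Rash.
2. Move 195083004 from Atrial fibrillation to Ventricular fibrillation. Its entries under Cardiac fibrillation and Cardiac flutter can stay.
3. Reconcile the injection-site terms with the administration-site outcome in Section 4, the Section 5.5.5 event list and Table 3 together. If the four terms move there, the Injury outcome has no listed event left, so its content must be restated.
4. Pass the pustulosis row under DRESS and the identifier 31048100 to the planned code review as queries only.

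The cost is an edit of the lists and a re-run of the affected outcome queries, because Section 15 shows that programming had already begun. No new data are needed.

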**Second step:** Medical charts include the physician notes, laboratory results, EEG recordings and any other original and detailed information that will be used to evaluate or validate the study outcomes. To improve the validity of medical chart review results, at each site these chart reviews will be conducted by experienced healthcare personnel (e.g. nurse clinician) who will be given standardized training before starting the review and a manual of procedures and code set index for assistance. In the case of any queries, an experienced neurologist will be consulted.

The quality control process used to set up the common dataset is described in section 5.7.

The hierarchical level of final reporting of the adverse event outcomes will be agreed with the UCB safety physicians attached to each UCB product, but initially will be reported to include all events. Those not listed (as being specific to LCM) will be included under Section 5.5.1.1 – other diagnoses. In this way all events are captured.

A selection of patients (approximately 10%) will have their charts reviewed (proportion to be agreed post evaluation of final patient numbers and quality of data). As these are retrospective deidentified data, no patient or family consent is required. UCB will not be party to any personal information regarding patients such as name, address or any other identifying variable. Only pertinent medical and treatment data will be collected.

The medical chart reviewers will not be blinded to IV LCM dosage contained within the patient notes as they need to assess dose so that patients can ultimately be categorised into treatment groups at the time of analysis. However, to avoid observation bias, they will be blinded to the full study protocol including title, objectives, and to how study group assignment criteria are applied. Instead, they will be provided instructions as to how to perform data extraction and provided with a case report form to complete. It is assumed based on clinical practice that the information in the medical charts will only indicate the dosage that was prescribed to the patients and will not include language relating to “loading dose/higher dose or recommended dose” per se. Therefore, blinding the medical chart reviewers to the full protocol, will minimize the risk for ascertainment bias.

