Paraplegic gait (finding)	SCTID: 250035005
On examination - gait spastic (finding)	SCTID: 163685000
On examination - limping gait (finding)	SCTID: 163691003
Investigations	
ECG PR Prolonged	
Electrocardiogram: partial atrioventricular block - long PR (finding)	SCTID: 164902006
Prolonged PR interval (finding)	SCTID: 164947007
Injury, poisoning and procedural complications	
Injection site discomfort	
Injection site burning (disorder)	SCTID: 95389008
Injection site reaction (disorder)	SCTID: 95377006
Injection site disorder (disorder)	SCTID: 95376002

Table 3 SNOMED-CT concepts for the study	
Study outcome	SNOMED code
Injection site dermatitis (disorder)	SCTID: 95393002
Injection site urticaria (disorder)	SCTID: 95394008
Injection site edema (disorder)	SCTID: 95392007
Swelling at injection site (disorder)	SCTID: 213340005
Injection site inflammation (disorder)	SCTID: 95391000
Injection site induration (disorder)	SCTID: 95402002
Induration at injection site (disorder)	SCTID: 213337005
Injection site hypersensitivity (disorder)	SCTID: 95378001
Injection site cyst (disorder)	SCTID: 95396005
Injection site mass (disorder)	SCTID: 95395009
Injection site ulcer (disorder)	SCTID: 95400005
Injection site abscess (disorder)	SCTID: 95382004
Injection site atrophy (disorder)	SCTID: 95404001
Injection site necrosis (disorder)	SCTID: 95397001
Injection site fibrosis (disorder)	SCTID: 95403007
Injection site bruising (disorder)	SCTID: 95401009
Injection site infection (disorder)	SCTID: 95381006
Injection site granuloma (morphologic abnormality)	SCTID: 24389009
Injection site thrombosis (disorder)	SCTID: 95386001
Injection site hemorrhage (disorder)	SCTID: 95385002
Injection site paresthesia (disorder)	SCTID: 95399003
Injection site nerve damage (disorder)	SCTID: 95390004
Injection site malabsorption (disorder)	SCTID: 95387005
Injection site extravasation (disorder)	SCTID: 95384003
On examination - Injection sites abnormal (disorder)	SCTID: 308092004
Injection site sterile abscess (disorder)	SCTID: 95383009
Injection site pigmentation change (disorder)	SCTID: 95380007
Application AND/OR injection site disorder	SCTID: 95363008
Application site rash (disorder)	SCTID: 95371007
Injection site pain (disorder)	SCTID: 95388000
Erythema at injection site (disorder)	SCTID: 213338000
Injection site irritation (disorder)	SCTID: 95379009
Injection site erythema	

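### The Table 3 list for the primary outcome Hypersensitivity has one general allergic drug reaction code but no anaphylaxis, angioedema, urticaria or drug-eruption code, so the outcome is likely under-counted

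*Protocol*

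**What the plan says.** Section 5.5.1 makes Hypersensitivity a primary variable: "The incidence rate and incidence rate ratio of hypersensitivity (selected PTs as described in Section 5.5.5"). Section 5.5.5 then names specific events for six of the system organ classes and none for Hypersensitivity. What remains as a definition is the Hypersensitivity block at the end of Table 3, which holds five concepts:

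- "Non-allergic drug hypersensitivity disorder (disorder")
- "Hypersensitivity disease of liver caused by drug (disorder")
- "Renal hypersensitivity caused by drug (disorder")
- a general code for an allergic reaction to a medicine that was correctly chosen and given
- DRESS

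Other codes that are allergic or hypersensitivity reactions by name stand elsewhere in the table. "Urticaria medicamentosa (disorder") and allergic urticaria are under Urticaria. "Drug-aggravated angioedema-urticaria (disorder") is under both Angioedema and Urticaria. Eruption caused by drug is under Rash. Cutaneous hypersensitivity is under Rash and again under severe cutaneous adverse reactions. "Injection site hypersensitivity (disorder") is under Injection site discomfort.

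For events outside the lists, Section 5.4.1 says: "Those not listed (as being specific to LCM) will be included under Section 5.5.1.1", as other diagnoses. Neither the table of contents nor the text has a section with that number. Section 5.5.5 also says that the Table 3 concepts will be reviewed and that case definitions will be developed with clinicians.

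**The concern.** A primary outcome named Hypersensitivity should collect the reactions that a clinician would call hypersensitivity. As printed, it collects them only if they were recorded under the general allergic-reaction code, as an organ-specific or non-allergic drug hypersensitivity, or as DRESS. A reaction recorded only by its manifestation goes elsewhere, and one manifestation, anaphylaxis, goes to no listed outcome at all.

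Two results are at stake. The Hypersensitivity rate in each dose group may come out too low. A difference between dose groups in anaphylaxis might also not show in any primary rate or rate ratio.

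**Working it through.** The protocol gives no figure to reproduce here. The check is a comparison of code lists, all taken from Table 3, Section 5.5.5.

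**Step 1. Overlap of the five Hypersensitivity codes with the related lists**

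| List in Table 3 | Codes in list | Also under Hypersensitivity |
|---|---|---|
| Angioedema | 4 | 0 |
| Urticaria | 13 | 0 |
| Rash: codes naming an eruption caused by a drug | 4 | 0 |
| Cutaneous hypersensitivity | 1 | 0 |
| Injection site hypersensitivity and injection site urticaria | 2 | 0 |
| DRESS | 2 | 1 (702809001) |
| Severe cutaneous adverse reactions | 10 | 1 (the same code) |

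Two codes are shared by the angioedema and urticaria lists, so the first three rows hold 4 + 13 − 2 + 4 = 19 distinct codes. None of the 19 is under Hypersensitivity. Not all 19 are allergic (chronic and dermatographic urticaria, for example), so 19 is not a count of missing codes.

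**Step 2. Anaphylaxis.** Anaphylaxis or anaphylactic shock concepts in the whole of Table 3: 0.

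**Step 3. Whether single counting explains the gap.** It does not. DRESS is listed under three outcomes (DRESS, severe cutaneous adverse reactions, Hypersensitivity). The Stevens-Johnson and toxic epidermal necrolysis codes are listed under Skin and under severe cutaneous adverse reactions. The table therefore already lets one code serve several outcomes.

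**Step 4. Where a child is counted, with the lists applied as printed**

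| How the reaction is coded | Hypersensitivity | Other primary outcome |
|---|---|---|
| General allergic drug reaction | yes | none needed |
| Angioedema, urticaria or drug eruption only | no | Skin |
| Cutaneous hypersensitivity only | no | Skin; severe cutaneous adverse reactions |
| Injection site hypersensitivity only | no | Injury, poisoning and procedural complications |
| Anaphylaxis only | no | none |

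**Step 5. Effect on the estimates.** Let s be the share of hypersensitivity cases that carry one of the five listed codes. The expected rate is then about s times the true rate. If s is the same in both dose groups it cancels from the rate ratio, and the loss is one of events and so of precision. If s differs between the groups, for instance because anaphylaxis makes up a larger part of the reactions in one of them, the ratio shifts too. The protocol gives no code frequencies, so s cannot be set.

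**The case against.** The strongest reply has four parts.

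- **The list does hold a general allergic drug reaction code.** This stands. A reader might infer that acute allergic reactions are not counted under Hypersensitivity at all, and the table does not support that. What is missed is the reaction recorded only under a specific term.
- **Most of these reactions already count in a primary outcome.** This also stands. Angioedema, urticaria and drug eruption enter Skin, a primary outcome. Angioedema, urticaria and rash are also secondary outcomes with their own rates and ratios (Section 5.5.2). For them the problem is an incomplete Hypersensitivity rate, not a lost event. The reply does not reach anaphylaxis.
- **Table 3 is provisional, and other safeguards exist.** This stands in part. The concept review is the natural place for the correction, but it is described as a review of the concepts listed, and anaphylaxis is not among them. Section 5.1 plans chart review for all eligible patients, which could find such cases, but Section 5.4.1 reduces it to about 10%. For patients without chart review, Section 5.9.2 takes an unrecorded diagnosis as absent. The one specified sensitivity analysis of outcome definitions (Section 5.9.1.4) adds a related medication or procedure code and no diagnoses. The category for other diagnoses would capture anaphylaxis, but outside the primary rates.
- **Descendants of a listed concept might be retrieved.** The protocol does not say so, and Table 3 prints narrower concepts row by row, as for atrial fibrillation. This remains an assumption.

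A reader might also infer that allergic reactions are especially expected after an IV dose, that the true rate is several times the one that will be reported, or that the list departs from the standard MedDRA query. The documents support none of these. Section 5.9.4 says only that most events are anticipated within 24 hours, there is no basis for a numerical share, and the content of the query is not given.

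**Conclusion.** The point holds in a limited form. The five-concept list leaves anaphylaxis out of every primary rate when it is the only code recorded. It also leaves angioedema, urticaria, drug eruption, cutaneous hypersensitivity and injection site hypersensitivity out of the Hypersensitivity outcome, although these still count elsewhere. Hypersensitivity is likely under-counted, and the size cannot be estimated from the documents.

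This rests on two assumptions: that the codes are matched as printed, without descendants, and that some reactions are recorded only under a specific manifestation. The misplaced rows and codes at the end of the table come from text extraction and are not part of the point. The reference to a non-existent Section 5.5.1.1 is a separate, minor defect.

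**What to change.** In the review of Table 3 concepts that Section 5.5.5 already plans:

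1. Add anaphylaxis and anaphylactic shock concepts to Hypersensitivity. The codes have to be selected, since none is printed.
2. List under Hypersensitivity as well the codes already printed for angioedema, allergic and drug urticaria (including drug-aggravated angioedema-urticaria), eruption caused by drug, cutaneous hypersensitivity and injection site hypersensitivity. Keep them in their present outcomes. Leave clearly non-allergic rash and urticaria codes out.
3. Count each child once within Hypersensitivity, in line with the first-occurrence rule of Section 5.9.1.2.

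**Cost.** Section 15 shows that programming had already begun, so this means a code-list change and a re-run. If the change is judged significant, it also needs an amendment under Section 11.4. Some children will count under both Skin and Hypersensitivity, so the two counts must not be added together. The same overlap already exists across outcomes for DRESS.
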